7.4 Lipase and amylase elevations

To ensure patient safety and enhance the reliability in determining the potential for pancreatic events with bimagrumab, a standardized process for identification, monitoring and evaluation of pancreatic events has to be followed ([Table 7-2](#)).

[figure not shown]

Table 7-2 Safety monitoring guidance for amylase and lipase elevations

Event	Follow up monitoring
Lipase and/or amylase < 3x ULN	
 • If asymptomatic, follow up at discretion of investigator. • If clinical symptoms (e.g., abdominal pain, nausea, diarrhea) suggest pancreatic involvement, re-check enzymes (amylase, lipase) and inflammatory markers (C-reactive protein) and consider pancreatic imaging (i.e., abdominal ultrasound or CT or MRI) to evaluate for presence of pancreatitis.
Lipase and/or amylase ≥ 3x ULN	
 • Re-check enzymes (amylase, lipase) and inflammatory markers (C-reactive protein) independent of presence of clinical symptoms. • Assess subject for clinical symptoms. • Conduct pancreatic imaging (i.e. abdominal ultrasound or CT or MRI) to evaluate for presence of pancreatitis. • Study drug interruption based on findings of additional assessments and at discretion of investigator.

As defined in [Section 7.1](#), medically significant events which are considered as serious adverse events (SAEs) should follow the standard procedures for SAE reporting as described in [Section 7.2](#). Every pancreatic event reported as an SAE should include a causality assessment of the event via exclusion of alternative causes (e.g., gallstones, co-medication).

An investigation of the pancreas needs to be followed up until resolution. A gastroenterology consult can be included at the investigator’s discretion. All follow-up information, and the procedures performed, should be recorded in the appropriate CRFs.

7.5 Pregnancy reporting

Not applicable in this study where only post-menopausal women will be enrolled.

8 Data review and database management

8.1 Site monitoring

Before study initiation, at a site initiation visit or at an investigator’s meeting, a Novartis representative will review the protocol and CRFs with the investigators and their staff. During the study, the field monitor will visit the site regularly to check the completeness of patient records, the accuracy of entries on the CRFs, the adherence to the protocol and to Good Clinical Practice, the progress of enrollment, and to ensure that investigational treatment is being stored, dispensed, and accounted for according to specifications. Key study personnel must be available to assist the field monitor during these visits.

The investigator must maintain source documents for each patient in the study, consisting of case and visit notes (hospital or clinic medical records) containing demographic and medical information, laboratory data, electrocardiograms, and the results of any other tests or assessments. All information on CRFs must be traceable to these source documents in the patient's file. The investigator must also keep the original informed consent form signed by the patient (a signed copy is given to the patient).

The investigator must give the monitor access to all relevant source documents to confirm their consistency with the CRF entries. Novartis monitoring standards require full verification for the presence of informed consent, adherence to the inclusion/exclusion criteria, documentation of SAEs, and of data that will be used for all primary variables. Additional checks of the consistency of the source data with the CRFs are performed according to the study-specific monitoring plan. No information in source documents about the identity of the patients will be disclosed.

8.2 Data collection

Designated investigator staff will enter the data required by the protocol into the OC/RDC system. Designated investigator site staff will not be given access to the system until they have been trained.

Automatic validation procedures within the system check for data discrepancies during and after data entry and, by generating appropriate error messages, allow the data to be confirmed or corrected online by the designated investigator site staff. The Investigator must certify that the data entered into the electronic Case Report Forms are complete and accurate. After database lock, the investigator will receive copies of the patient data for archiving at the investigational site.

8.3 Database management and quality control

Novartis staff or CRO working on behalf of Novartis will review the data entered into the CRFs by investigational staff for completeness and accuracy and instruct the site personnel to make any required corrections or additions. Queries are sent to the investigational site using an electronic data query. Designated investigator site staff is required to respond to the query and confirm or correct the data. If the electronic query system is not used, a paper Data Query Form will be faxed to the site. Site personnel will complete and sign the faxed copy and fax it back to Novartis staff that will make the correction to the database. The signed copy of the Data Query Form is kept at the investigator site.

Concomitant medications entered into the database will be coded using the WHO Drug Reference List, which employs the Anatomical Therapeutic Chemical classification system. Concomitant procedures, non-drug therapies and adverse events will be coded using the Medical dictionary for regulatory activities (MedDRA) terminology.

Laboratory samples will be processed centrally and the results will be sent electronically to Novartis (or a designated CRO).

ECG readings, all imaging (echocardiography, DXA and X-ray) will be processed centrally and the results will be sent electronically to Novartis (or a designated CRO).

Randomization codes and data about all study drug(s) dispensed to the patient and all dosage changes will be tracked using an Interactive Response Technology (IRT). The system will be supplied by a vendor, who will also manage the database. The database will be sent electronically to Novartis (or a designated CRO).

Each occurrence of a code break via IRT will be reported to the clinical team and monitor. The code break functionality will remain available until study shut down or upon request of Novartis.

The occurrence of relevant protocol deviations will be determined. After these actions have been completed and the database has been declared to be complete and accurate, it will be locked and the treatment codes will be unblinded and made available for data analysis. Any changes to the database after that time can only be made after written agreement by Novartis Development management.

At the time of the primary analysis, which will occur when all patients will have completed the double-blind treatment epoch (Week 24 visit), similar actions will be completed and the treatment codes will be made available to the Novartis global study team for data analysis..

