5.4 Treatment blinding

Patients, investigators and their site personnel (with exception of the unblinded pharmacist), as well as Novartis agents in the countries as well as the global study team involved in the routine conduct of the trial will remain blinded to the identity of the individual patient treatment from the time of randomization until the final database lock (when all patients will have completed both the Treatment epoch and the Post Treatment Follow-Up epoch)..

For the study duration, the following method will be used to maintain the blind:

1. Randomization data will be kept strictly confidential until the time of unblinding, and will not be accessible to anyone else involved in the study with the following exceptions:
 - specific vendors whose role in trial conduct requires their unblinding [e.g., Interactive Response Technology (IRT)]
 - DSM (drug supply management)
 - members of the DMC
 - study bioanalyst [REDACTED]
 - an independent, unblinded pharmacist/designee at the investigator's site who will prepare investigational treatment infusion
- [REDACTED]

- unblinded monitor who will perform investigational treatment accountability at the site
 - An independent global clinical person will have access to individual randomization codes at the interim database lock for the primary analysis
2. The identity of the treatments will be concealed by the use of investigational treatments in forms of infusion bags filled with bimagrumab or placebo and covered with a sleeve that are identical in appearance, labeling and schedule of administration. However, the bimagrumab and placebo vials will be supplied “open-label” to the unblinded pharmacist.
 3. Results of DXA scans and a mechanism of action related biomarker (activin A) as well as FSH that may reveal [REDACTED] effects of the study drug will not be shared by the central reader/laboratory to investigators, site staff or global study team but will be stored in a blinded part of the study data base.

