Due to the difference in supply and preparation methods of the active drug and placebo, an independent, unblinded pharmacist or designee who is independent of the study team will be required to maintain the blind. The unblinded pharmacist will receive the medication numbers, prepare infusions with either investigational drug or placebo, without disclosing the identity to any other site personnel. Appropriate measures must be taken by the unblinded pharmacist to ensure that the study team remains blinded throughout the course of dose administration and the remainder of the study. No other person will have access to the medication and drug administration documentation, except the unblinded monitor.

The unblinded pharmacist is NOT allowed to administer the drug to the patient.

Unblinded monitors will be required to perform proper oversight for drug accountability. The unblinded field monitor will be responsible exclusively for drug accountability and must take appropriate measures to ensure the blind is preserved for the duration of the study.

Full unblinding (treatment and dose) will only occur in the case of patient emergencies and at the conclusion of the study.

In the case of unblinding, the patient will be discontinued from investigational treatment and enter the Post-treatment follow-up epoch. Discontinuation of investigational treatment and premature patient discontinuation are discussed in detail in [Section 5.5.9](#).

Following the interim database lock, to perform the primary analysis, partial unblinding will occur as follows:

- An independent global clinical person will have access to individual randomization codes after the primary analysis.
- The Novartis global study team will be unblinded to the group level results only
- The study subjects and the site personnel will remain blinded until the final database lock

The study bioanalyst will have access to the randomization list to facilitate analysis of samples (i.e. to avoid the unnecessary analysis of placebo samples). [REDACTED]

[REDACTED] The bioanalyst will provide sample data to the team under blinded conditions [REDACTED]

██████████ The unblinded bioanalyst ██████████ will keep treatment allocation information confidential until clinical database lock.

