2.4.2 Final update analysis

Additional efficacy and safety data will be recorded from Week 24 to Week 48. During the post-treatment follow-up epoch patients, the Novartis global study team and investigative centers will still be blinded to the treatment received in the treatment epoch. When all patients have completed the post-treatment follow-up epoch (Week 48 [EOS] assessments regardless of study completion or premature discontinuation), the database will be finally locked (clean state of all data expected) and the final update analysis will be performed. Any data collected in the post-treatment follow-up epoch as indicated in the programming notes in RAP Module 7 (CSR Deliverables) will be revisited, finalized and authorized at the time of the final update analysis.

At the time of the primary analysis (Week 24), any additional efficacy and safety data available in the post-treatment follow-up epoch, will be summarized in a similar manner as planned for the final update analysis, i.e. relative to the number of patients with data collected in the post-treatment follow-up epoch as described in [Section 2.4.1](#) (Primary analysis).

The same convention in view of patients entering the post-treatment follow-up epoch will apply at the time of the final update analysis.

Furthermore, the same data handling conventions as described in [Section 2.3](#) (Treatment pooling and data handling of pre-amendment 2) will be applied with regards to treatment-emergent and concomitant definitions.

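### Protocol 8.3 gives the treatment codes to the Novartis global study team at the Week 24 lock, whereas Protocol 5.4, 9 and 9.2 and SAP 2.4 limit that team to group-level results

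*Protocol*

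**What the plan says.** Protocol 8.3 describes two locks. At the end of the study, once the database is declared complete, "it will be locked and the treatment codes will be unblinded and made available for data analysis". The section then turns to the primary analysis, held when all patients have completed Week 24. It says similar actions will be taken and "the treatment codes will be made available to the Novartis global study team for data analysis". It sets no group-level limit.

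Protocol 5.4, the section devoted to blinding, says otherwise. It states that "the global study team involved in the routine conduct of the trial will remain blinded to the identity of the individual patient treatment", and gives the period as "from the time of randomization until the final database lock", that is, after both the treatment and follow-up epochs. For the interim lock it specifies partial unblinding: "The Novartis global study team will be unblinded to the group level results only". The one global role given individual codes is separate: "An independent global clinical person will have access to individual randomization codes after the primary analysis". Protocol 9 and 9.2 also describe the unblinding of the global study team as being at group level.

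SAP 2.4.1 assigns patient-level unblinding for the primary analysis to a biostatistics team (its name is redacted) and restricts selected members of the Novartis global team to group level. SAP 2.4.2 adds that during follow-up "the Novartis global study team and investigative centers will still be blinded to the treatment received in the treatment epoch".

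**The concern.** The protocol gives two incompatible instructions about who holds patient-level codes while the trial is still running. The primary analysis takes place when the last patient reaches Week 24, and follow-up runs to Week 48, so up to 48 − 24 = 24 weeks of follow-up can remain for the latest patients. A release of codes cannot be undone.

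What is at stake is sponsor-side judgement on data that are still open after the interim lock: which queries are raised, which events are picked out for adjudication, and which deviations remove a patient from a per-protocol set. Such decisions should be taken without knowledge of the patient's arm. The post-treatment effect on SPPB and gait speed up to End of Study is a stated secondary objective (Protocol 2.2), so the follow-up data matter.

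**Working it through.** No arithmetic applies beyond the follow-up interval. The check is a comparison of texts.

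**1. What each place says about the global study team at the interim lock**

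| Place | Access given |
|---|---|
| Protocol 8.3 | Treatment codes, for data analysis |
| Protocol 5.4, opening paragraph | None to individual treatment until final lock |
| Protocol 5.4, partial unblinding rules | Group-level results only |
| Protocol 9 and 9.2 | Group-level unblinding |
| SAP 2.4.1 | Group level only, for selected members |
| SAP 2.4.2 | Still blinded to treatment received during follow-up |

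Of these, 8.3 alone releases codes to this team.

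**2. Could the codes in 8.3 mean group-level output?** Not on the wording. The same section uses the same term for the end of the study, where it plainly means patient-level assignment, and then calls the Week 24 steps similar. Group-level results are not codes.

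**3. Is the sentence in 8.3 current?** Yes. It stands in the body of the protocol. The Amendment 4 summary lists an unblinding change for 5.4 and Section 9 and does not list 8.3. That 8.3 was overlooked is a reasonable inference, but only an inference.

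**4. Which rule is intended?** SAP 2.4.1 suppresses minima, maxima and any subgroup level with fewer than five patients, so that the selected Novartis team members are not inadvertently unblinded. Protocol 5.4 withholds DXA, activin A and FSH results from the global study team. The SAP 2.4.1 safeguard would serve no purpose if the same people held the codes, so the intended rule is the one in 5.4.

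**5. What is still open after the interim lock?**
- Adverse event and concomitant medication data are only as clean as feasible, and post-Week 24 visit data are accepted as not clean or locked (SAP 2.4.1).
- Queries and corrections continue (Protocol 8.3).
- The database is searched for events to send for follow-up and adjudication (Protocol 8.5).
- The Modified PP set is finalised before the final update analysis. SAP 2.7 requires a blinded data review for the PP set but does not say so for the Modified PP set.

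**6. What is not exposed?**
- Patients and site personnel stay blinded until final lock (Protocol 5.4, SAP 2.4.1). SPPB, gait speed and falls at Weeks 36 and 48 are collected at sites (Protocol 6.4.2 to 6.4.4).
- Adjudicators review events blindly (Protocol 8.5).
- Efficacy analyses based on the 24-week epoch are expected to be final at the primary analysis (SAP 2.4.1).
- The fixed sequence uses Week 24 gait speed and SPPB, then falls observed up to the primary analysis (SAP 2.10.2.3).

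The tests are called largely rather than wholly unaffected because of falls. That comparison includes data beyond Week 24, and falls are entered on the adverse event form (Protocol 6.4.4), whose data are not final at that lock.

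**The case against.** The strongest reply is that one stray sentence is outweighed. The dedicated blinding section gives specific rules for this very lock, Protocol 9 and 9.2 and the SAP agree with it, and SAP 2.4.1 refers to a separate unblinding plan with the details. Harm would require staff to follow 8.3 and disregard all of these. This argument stands as far as likelihood goes. It does not remove the conflict: 8.3 remains an operative instruction in the section on database lock, and a plan outside the protocol does not correct it.

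A reader might infer that Week 48 function, falls and adjudicated safety would cease to be double-blind. The documents do not support that. The measurements are made by blinded sites on blinded patients, and the adjudication committee reviews blindly whatever happens under 8.3. Only the selection of events sent to it lies upstream.

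A reader might also infer that the global study team itself handles queries, deviations and event selection. The documents give queries to Novartis staff or a CRO (Protocol 8.3), deviations to the Novartis clinical team (SAP 3.10) and event searches to the clinical team (Protocol 8.5). Overlap with the global study team is plausible but is nowhere stated.

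**Conclusion.** The contradiction is real and in current text. It is an internal inconsistency rather than a flaw in the intended design, which is clear everywhere else. It is worth correcting because following 8.3 as written would break the blind that 5.4 sets up.

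Its reach is limited to sponsor-side handling of data still open between the interim and final locks: cleaning of adverse event, concomitant medication and post-Week 24 data, the search for adjudicable events, and the Modified PP set. No sample size, power or alpha figure changes, and the Week 24 primary and fixed-sequence results are not materially at risk.

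The conclusion rests on two assumptions. One is that the codes in 8.3 are patient-level, as the parallel sentence in that section indicates. The other is that at least some global study team members do the open work listed above. If none do, the practical effect is small and the point is one of consistency only.

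**What to change.** Amend Protocol 8.3 so that at the interim lock patient-level codes are released only to the biostatistics team described in SAP 2.4.1 and to the independent global clinical person described in Protocol 5.4, with the global study team receiving group-level results only.

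Two alignments in 5.4 should go with it:
- The visible list of those with access to randomization data does not mention that biostatistics team. It may be covered by the entry for vendors or by redacted text. If it is not, add it. The new 8.3 wording should not call this team independent, since the SAP does not describe it so.
- The access list lets the clinical person have individual codes at the interim lock, while the partial unblinding rules, like SAP 2.4.1, say after the primary analysis. State one time point.

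The cost is one rewritten sentence in 8.3 and at most two short edits in 5.4. Visits, data collection and analyses are unchanged.

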8.4 Data Monitoring Committee

An independent, program-wide DMC is instituted for bimagrumab with focus on safety.

The DMC will periodically review the safety information throughout the study to monitor the trial's progress for unexpectedly large differences in the incidence of AE/SAE between treatment groups.

The DMC for the study will be composed of individuals with experience and expertise in the management of patients with muscle wasting diseases and in the monitoring of randomized clinical trials as well as a DMC statistician. None of the DMC members will be involved in the operational conduct of the study or any other bimagrumab clinical or pre-clinical study, except as a member of the DMC.

The mission of the DMC will be to independently review and evaluate the unblinded safety data generated during the study as defined in this protocol. The DMC must also ensure that study participants are not exposed to unnecessary or unreasonable risks and that the study is conducted with high scientific and ethical standards. Finally, the DMC must make recommendations to the Sponsor on the actions to be taken on the study, which may include the following:

[figure not shown]
- Discontinuation of the study.
- Suggested modifications to the study protocol and/or the informed consent document.
- Continuation of the study according to the protocol and the relevant amendments.

The DMC is accountable to the Sponsor for appropriate monitoring of the study data.

Although the DMC may make recommendations to the Sponsor about changes in the conduct of the study, final decisions will be made by Novartis. In the case of early termination, consultation with Health Authorities may be required.

Members of the DMC will not share any unblinded information with anyone outside of the DMC. Particularly, the Sponsor will remain fully blinded to any results throughout the study unless the DMC recommends changes in the conduct of the study (for example, early termination due to negative safety findings).

An independent statistical reporting team not involved in the conduct of the studies will prepare the information for the DMC according to the specifications from the DMC statistician. The main tasks may include:

- Generation of unblinded outputs for the DMC including tables, figures, and listings, as required.
- Preparation of any other reports requested by the DMC during the closed session.
- Review of the unblinded reports before sending to the DMC.

The frequency of the DMC meetings will be determined by the members and ratified in the DMC Charter.

